5.5.1 Occurrence of Serious Adverse Events

(1) Patients included in tabulation/analysis

Patients included in safety evaluation

(2) Data tabulated/analyzed

The following variables will be tabulated:

Variable	Data tabulated/analyzed
Number of patients with a SAE	Number of patients who experienced a SAE
Number of SAE	Number of reported SAE Multiple episodes of the same SAE (PT) in the same patient will be tabulated as the total number of episodes.
Incidence of SAE	The incidence of SAE will be calculated as number of patients with a SAE/number of patients included in safety evaluation × 100.
Type of SAE	SAEs will be classified by SOC and then tabulated by PT. For laboratory tests, SAEs will be classified by SOC, then sorted by HLT, and finally tabulated by PT. For SOC, the number of patients with a SAE and the incidence of SAE will be listed by SOC internationally agreed order. For PT, the number of patients with a SAE and the incidence of SAE will be listed in ascending order of PT code. Multiple episodes of the same SAE (PT) in the same patient will be tabulated as 1 patient. The number of patients with a SAE not related to Zacro will be presented in parentheses.

(3) Table/figure number

Table 5.5-1

5.5.2 Occurrence of Serious Adverse Drug Reactions/Infections

(1) Patients included in tabulation/analysis

Patients included in safety evaluation

(2) Data tabulated/analyzed

The following variables will be tabulated:

Variable	Data tabulated/analyzed
Number of patients with a serious ADR, etc.	Number of patients who experienced a serious ADR, etc.
Number of serious ADR,	Number of reported serious ADR, etc.

etc.	Multiple episodes of the same serious ADR, etc. (PT) in the same patient will be tabulated as the total number of episodes.
Incidence of serious ADR, etc.	The incidence of serious ADR, etc. will be calculated as number of patients with a serious ADR, etc./number of patients included in safety evaluation $\times 100$.
Type of serious ADR, etc.	
Serious ADRs, etc. will be classified by SOC and then tabulated by PT. For laboratory tests, serious ADRs, etc. will be classified by SOC, then sorted by HLGT, and finally tabulated by PT.
 
For SOC, the number of patients with a serious ADR, etc. and the incidence of serious ADR, etc. will be listed by SOC internationally agreed order.
 
For PT, the number of patients with a serious ADR, etc. and the incidence of serious ADR, etc. will be listed in ascending order of PT code.

(3) Table/figure number

Table 5.5-2

5.6 Listing of Occurrence of Serious Adverse Events and Serious Adverse Drug Reactions/Infections in Patients Excluded from Safety Evaluation

5.6.2 Occurrence of Serious Adverse Drug Reactions/Infections

(1) Patients included in tabulation/analysis

Patients included in safety evaluation

(2) Data tabulated/analyzed

The following variables will be tabulated:

Variable	Data tabulated/analyzed
Number of patients with a serious ADR, etc.	Number of patients who experienced a serious ADR, etc.
Number of serious ADR, etc.	Number of reported serious ADR, etc. Multiple episodes of the same serious ADR, etc. (PT) in the same patient will be tabulated as the total number of episodes.
Incidence of serious ADR, etc.	The incidence of serious ADR, etc. will be calculated as number of patients with a serious ADR, etc./number of patients included in safety evaluation × 100.
Type of serious ADR, etc.	Serious ADRs, etc. will be classified by SOC and then tabulated by PT. For laboratory tests, serious ADRs, etc. will be classified by SOC, then sorted by HLTG, and finally tabulated by PT. For SOC, the number of patients with a serious ADR, etc. and the incidence of serious ADR, etc. will be listed by SOC internationally agreed order. For PT, the number of patients with a serious ADR, etc. and the incidence of serious ADR, etc. will be listed in ascending order of PT code.

(3) Table/figure number

Table 5.6-2

5.7 Changes in Test/Measurement Data over Time

5.7.1 Vital Signs (Pulse Rate)

(1) Patients included in tabulation/analysis

Patients included in safety evaluation

(2) Data tabulated/analyzed

Analyses described below will be performed for patients who have relevant data both before and after treatment with Zacras.

For pulse rate (bpm), summary statistics will be calculated for measured values at each time point of measurement [at the start of treatment with Zacras, from 1 to 12 months of treatment with Zacras, and at the final assessment]. For the change from the start of treatment with Zacras, summary statistics will be calculated.

(3) Table/figure number

Table 5.7-1

5.7.2 Laboratory Tests

(1) Patients included in tabulation/analysis

Patients included in safety evaluation

(2) Data tabulated/analyzed

Analyses described below will be performed for patients who have relevant data both before and after treatment with Zacras.

For white blood cell count, platelet count, AST, ALT, γ -GTP, serum creatinine, BUN, and serum potassium, summary statistics will be calculated for test data at each time point of test [at the start of treatment with Zacras, from 1 to 12 months of treatment with Zacras, and at the final assessment]. For the change from the start of treatment with Zacras, summary statistics will be calculated.

(3) Table/figure number

Table 5.7-2

6.0 Tabulation/Analysis of Efficacy

6.1 Changes in Blood Pressure over Time

(1) Patients included in tabulation/analysis

Patients included in efficacy evaluation

(2) Data tabulated/analyzed

Analyses described below will be performed for patients who have relevant data both before and after treatment with Zacras.

For systolic and diastolic blood pressure, summary statistics and 95% CI for the mean will be calculated for test data at each time point of test [at the start of treatment with Zacras, from 1 to 12 months of treatment with Zacras, and at the final assessment]. The mean and standard deviation of test data will be illustrated.

In addition, the proportion of patients with normal blood pressure at each time point of test will be tabulated. The proportion of patients with normal blood pressure will be illustrated. A patient with normal blood pressure is defined as a patient meeting both criteria listed below. A patient with missing data on systolic and/or diastolic blood pressure will be handled as a patient with missing data.

- Systolic blood pressure <140 mmHg
- Diastolic blood pressure <90 mmHg

(3) Table/figure number

Table 6.1.1, Table 6.1.2, Figure 6.1.1, Figure 6.1.2

6.2 Changes in Blood Pressure over Time in Patients Who Switch from the Combined Use of Azilsartan and Amlodipine

(1) Patients included in tabulation/analysis

Patients included in efficacy evaluation who switch from combined use

(2) Data tabulated/analyzed

Analyses described below will be performed for patients who have relevant data both before and after treatment with Zacras.

For systolic and diastolic blood pressure, summary statistics and 95% CI for the mean will be calculated for test data at each time point of test [at the start of treatment with Zacras, from 1 to 12 months of treatment with Zacras, and at the final assessment]. For the change from the start of treatment with Zacras, summary statistics and 95% CI for the mean will be calculated. The mean and standard deviation of test data and change will be illustrated. The percentage change from the start of treatment with Zacras ((test data at each time point of test - test data at the start of treatment with Zacras) ÷ test data at the start of treatment with Zacras × 100), summary statistics will be calculated. The proportion of patients with normal blood pressure at each time point of test will be tabulated. The proportion of patients with normal blood pressure

will be illustrated.

(3) Table/figure number

Table 6.2.1, Table 6.2.2, Table 6.2.3, Figure 6.2.1-1, Figure 6.2.1-2, Figure 6.2.3

6.3 Changes in Blood Pressure over Time in Patients Except for Those Who Switch from the Combined Use of Azilsartan and Amlodipine

(1) Patients included in tabulation/analysis

Patients included in efficacy evaluation except for those who switch from combined use

(2) Data tabulated/analyzed

Analyses described below will be performed for patients who have relevant data both before and after treatment with Zacras.

For systolic and diastolic blood pressure, summary statistics and 95% CI for the mean will be calculated for test data at each time point of test [at the start of treatment with Zacras, from 1 to 12 months of treatment with Zacras, and at the final assessment]. For the change from the start of treatment with Zacras, summary statistics and 95% CI for the mean will be calculated, and the paired t-test will be performed. The mean and standard deviation of test data and change will be illustrated. For the percentage change from the start of treatment with Zacras, summary statistics will be calculated.

The proportion of patients with normal blood pressure at each time point of test will be tabulated. The proportion of patients with normal blood pressure will be illustrated.

(3) Table/figure number

Table 6.3.1, Table 6.3.2, Table 6.3.3, Figure 6.3.1-1, Figure 6.3.1-2, Figure 6.3.3

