3.0 Planned Sample Size and Rationale

3.1 Planned Sample Size

1,000 patients

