3.2 Rationale

Patient populations identified as important missing information from Japanese clinical studies of Zacras Combination Tablets are patients with renal impairment, patients with hepatic impairment, and elderly patients (≥ 75 years old). The sample size required to evaluate the safety and efficacy of long-term use of Zacras Combination Tablets in these patient populations was calculated by reference to previous results. More specifically, according to final tabulation (number of patients included in safety evaluation: 3,300) in a previous specified drug-use survey (long-term use survey in hypertension) of a fixed-dose combination (UNISIA Combination Tablets) of an angiotensin receptor blocker (ARB) (candesartan) and a Ca antagonist (amlodipine), which belongs to the pharmacologically same class as Zacras Combination Tablets, patients with renal impairment, patients with hepatic impairment, and elderly patients (and those ≥ 75 years old) accounted for 6.9%, 11.5%, and 65.2% (36.8%) of all patients, respectively. According to final tabulation (number of patients included in safety evaluation: 4,152) in a drug use-results survey of candesartan alone (BLOPRESS Tablets), patients with renal impairment, patients with hepatic impairment, and elderly patients (and those ≥ 75 years old) accounted for 9.5%, 10.6%, and 53.2% (22.1%), respectively. With a target sample size of 1,000 patients for the present survey, 70 patients with renal impairment, 100 patients with hepatic impairment, and 500 elderly patients (and 200 patients ≥ 75 years old)

are expected to be collected, probably allowing the safety and efficacy evaluation in these populations. This calculation is not based on statistical estimation.

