6.0 Planned Number of Medical Institutions by Department

Internal medicine and other departments Approximately 250 medical institutions

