9.1 Entries into the Patient Registration Form

1) Survey items

Name of the medical institution, name of a physician who completes the patient registration form, date of prescription of Zacras Combination Tablets, patient identification number, patient initials, sex, date of birth, assessment based on the inclusion criteria, assessment

based on the exclusion criteria, presence or absence of breast-feeding (only females)

2) Time points of survey

At patient registration

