1.3 Level of Significance, Confidence Coefficient

Level of significance: 5% (two-sided test)

Confidence coefficient: 95% (two-sided estimate)

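### The tabulated 95% CIs for mean blood pressure (SAP 6.1 to 6.4) and the paired t-test in 6.3 ignore institution, so they are somewhat too narrow or too liberal if patients within an institution are correlated.

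*SAP*

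**What the plan says.** The target in Protocol 3.1 is "1,000 patients", and Protocol 6.0 plans "Approximately 250 medical institutions". Protocol 7.3 has each investigator register the patients who are prescribed the drug. Protocol 8.0 closes registration once the overall target is met. No limit per institution is given.

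In the current SAP edition (printed first in the file):

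- **6.1** covers the whole efficacy set and concerns measured values only: "summary statistics and 95% CI for the mean will be calculated for test data at each time point of test".
- **6.2** covers patients who switch from combined use of the two ingredients. It gives CIs for measured values and for change, with no test.
- **6.3** covers the remaining efficacy patients. It gives CIs for measured values, and for change "summary statistics and 95% CI for the mean will be calculated, and the paired t-test will be performed".
- **6.4** gives CIs for final-assessment values by subgroup, with no test.

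SAP 1.3 sets a two-sided 5% level and 95% confidence. The figures in 6.1 to 6.3 show means with standard deviations.

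The current SAP uses institution only in 2.0, to count contributing sites. The identifier is available, because the registration form in Protocol 9.1 begins "Name of the medical institution, name of a physician who completes the patient registration".

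**The concern.** An ordinary CI for a mean, and an ordinary paired t-test, take the variance of the mean as the patient variance divided by the number of patients. That is right only if patients are independent. Patients at one institution share prescribers, staff, measuring equipment and prescribing habits, so a positive correlation is a reasonable expectation. If it is positive, the true variance of the mean exceeds the one used. An interval labelled 95% then covers less often than that, and a 5% test rejects more often than that.

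These intervals are the only precision statement attached to the blood pressure results. Section 6.2 is the most sensitive place. Its patients move from the same ingredients and doses to the combination tablet, so a mean change near zero is plausible, and an interval that is slightly too narrow could wrongly exclude zero.

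**Working it through.** **Is there a planned precision figure to reproduce?** No. The documents give no standard deviation, interval width, power, ICC or design effect for blood pressure. The only usable inputs are the 1,000 patients and the 250 institutions.

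**Inputs**

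- Average patients per institution: m = 1000/250 = 4 (Protocol 3.1 and 6.0).
- ICC: not in the documents; assumed 0.01, 0.05 and 0.10.
- Coefficient of variation (CV) of institution sizes: not in the documents; assumed 0 (equal sizes) and 1 (very unequal).

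**Formulas**

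- Design effect: DE = 1 + ((1 + CV²) × m − 1) × ICC. With m = 4 this is 1 + 3 × ICC for CV 0 and 1 + 7 × ICC for CV 1.
- Correct width divided by stated width: √DE.
- Actual coverage of the stated 95% interval: 2Φ(1.96/√DE) − 1. The actual rejection rate of a nominal 5% test is 100% minus this.

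**Section 6.1, taking the full 1,000 patients**

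| ICC (assumed) | CV 0: DE | Width ratio | Coverage | CV 1: DE | Width ratio | Coverage |
|---|---|---|---|---|---|---|
| 0.01 | 1.03 | 1.015 | 94.7% | 1.07 | 1.034 | 94.2% |
| 0.05 | 1.15 | 1.072 | 93.2% | 1.35 | 1.162 | 90.8% |
| 0.10 | 1.30 | 1.140 | 91.4% | 1.70 | 1.304 | 86.7% |

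At ICC 0 nothing changes.

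**Check by simulation.** With 250 institutions of 4 patients and 10,000 runs, the ordinary test rejected 5.0%, 7.1% and 8.3% of the time at ICC 0, 0.05 and 0.10. The formula gives 5.0%, 6.8% and 8.6%. The patient-level standard deviation stayed at 1.00 throughout, so bars drawn as standard deviations are not narrowed. A second simulation (250 institutions, 3,000 replicates, ICC 0.02 to 0.10, equal and unequal sizes) gave 88.3% to 94.1% coverage for ordinary intervals and 94.6% to 95.3% for institution-clustered ones. Its lowest ordinary value lies a little above the formula's 86.7%, so the top of the CV 1 range is approximate.

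**Sections 6.2 and 6.3.** These split the efficacy set, and the sizes of the parts are not given. As an illustration, 500 patients spread over all 250 institutions gives m = 2:

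- Equal sizes: DE = 1 + ICC. At ICC 0.05 and 0.10 the intervals should be √1.05 = 1.025 and √1.10 = 1.049 times as wide, and the 5% test rejects 5.6% and 6.2% of the time.
- CV 1: DE = 1 + 3 × ICC, so 1.072 and 1.140 times as wide.

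If the subset came from fewer institutions, m would be larger.

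**Section 6.4.** Take the 70 patients with renal impairment expected in Protocol 3.2, and assume that they are spread in proportion to institution size. Each then shares an institution with 3 × 69/999 = 0.21 others (CV 0) or 7 × 69/999 = 0.48 others (CV 1). At ICC 0.10, √1.021 and √1.048 give standard errors 1.0% and 2.4% larger.

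**On the mmHg scale.** With an assumed standard deviation of 15 mmHg and 1,000 patients, the stated half-width is 1.96 × 15/√1000 = 0.93. For ICC 0.01 to 0.10 it becomes 0.94 to 1.06 (CV 0) or 0.96 to 1.21 (CV 1).

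**The case against.** The best case for leaving the SAP alone has four parts.

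**The size is unknown.** It rests on an ICC and a spread of institution sizes that the documents do not give, and the largest figures take the top of both assumed ranges. This stands. A reader might infer that the intervals certainly cover less than 95%, or that the 14% to 30% widening applies throughout 6.1 to 6.4. The documents support neither. The direction depends on a positive ICC, and those percentages belong to 1,000 patients at 4 per institution.

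**The mechanism is weaker for change.** A constant offset from a shared device or measuring habit cancels in a within-patient difference, so an ICC plausible for measured pressure cannot simply be carried over to change. This also stands. It does not help 6.1 or 6.4, which analyse measured values only.

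**The target may be only the participating institutions.** Institutions are contracted at the sponsor's request, not sampled at random, so between-institution variance need not count. This does not stand. The objective in Protocol 2.0 is about hypertensive patients treated in routine care, not only about the contracted sites.

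**The survey is descriptive.** It has a single arm, the protocol plans tabulations, and of the sample size Protocol 3.2 says "This calculation is not based on statistical estimation". No decision rule hangs on these intervals. This limits the consequence, but an interval printed as 95% should still cover about 95%.

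Two further readings are tempting and wrong. One is that the plotted error bars are too narrow; they are standard deviations, which clustering leaves alone. The other is that a paired t-test is affected in every section; in the current edition it appears only in 6.3.

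**Conclusion.** The point holds as a modest, conditional one. As written, the CIs in SAP 6.1 to 6.4 and the 6.3 test take patients from about 250 institutions as independent. If the within-institution correlation is positive, the tabulated intervals are too narrow and the 6.3 test is mildly anti-conservative.

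The full-set figures for 6.1 are the upper end of the problem. The subsets and subgroups have fewer patients per institution, and change is probably less correlated than level. Equal institution sizes are the most favourable case for the SAP, and nothing in the protocol enforces them.

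The efficacy conclusion is unlikely to turn on this. In the 15 mmHg illustration, only a mean change between 0.93 and at most 1.21 mmHg would move across the significance line. This is a cheap improvement to the precision statements, not a flaw that undermines the survey.

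**What to change.** Add one sentence to the SAP: the 95% CIs for the mean in 6.1 to 6.4, and the test of mean change in 6.3, use standard errors that are robust to clustering by institution, with a t reference on the number of contributing institutions minus 1. For each table, report the number of contributing institutions and the distribution of patients per institution.

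Keep the arithmetic means and all descriptive statistics, including the plotted standard deviations. A random institution intercept is not a good substitute. With unequal sizes it reweights the mean, so its interval need not centre on the tabulated value.

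The robust standard error needs no assumed ICC and no new data, since institution is recorded at registration. If the correlation is near zero, the intervals hardly change. The cost is a few lines of code and somewhat wider intervals. In a 6.4 category drawn from only a handful of institutions, the robust standard error is itself imprecise, which is a further reason to print the institution count beside it.

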1.0 Definitions of Terms, etc. and Handling of Test/Measurement Data

1.1 Definitions

Term	Definition
Zacras	Zacras Combination Tablets are abbreviated as Zacras in this document.
SOC	System organ class listed in the MedDRA/J
HLGT	High level group term listed in the MedDRA/J
PT	Preferred term listed in the MedDRA/J
LLT	Lowest level term listed in the MedDRA/J
Enrolled patient	Patient allowed to be enrolled
Patient from whom the CRF is collected	Patient from whom the CRF has been obtained
Patient from whom the CRF is not collected	Enrolled patient from whom the CRF has not been collected
Finalized patient	Patient from whom the CRF is collected who has the date of CRF completion entered into the PMS system or who requires no information on the CRF status and has not been excluded from the survey
Non-finalized patient	Patient from whom the CRF is collected who has not been finalized
Patient included in safety evaluation	Finalized patient who is included in safety evaluation
Patient excluded from safety evaluation	Finalized patient who is excluded from safety evaluation
Patient included in efficacy evaluation	Patient included in safety evaluation who is included in efficacy evaluation
Patient excluded from efficacy evaluation	Patient included in safety evaluation who is excluded from safety evaluation
Presence or absence of change in daily dose of Zacras	“Yes” for patients with a change in daily dose between the start of treatment with Zacras and the final assessment
Duration of treatment with Zacras	End date of treatment with Zacras - start date of treatment with Zacras + 1
End date of treatment	End date of the final dose described in the column of the end date of treatment in the CRF; or start date of treatment + 360 days if the end date of treatment is not described in the CRF and there is a check for “ongoing at 12 months after the start of treatment with Zacras.”
Treatment completer	Patient with a duration of treatment with Zacras of \geq start date of treatment + 360 days
Treatment non-completer	Patient with a duration of treatment with Zacras of \leq start date of treatment +

Term	Definition
	359 days
Reason for discontinuation of treatment with Zacras	If the duration of treatment with Zacras is \leq start date of treatment + 359 days, the reason for discontinuation of treatment described in the column of details on the use of Zacras in the CRF will be employed. If the duration of treatment with Zacras is \geq start date of treatment + 360 days, the patient will be handled as a treatment completer; therefore, the reason for discontinuation of treatment described in the column of details on the use of Zacras in the CRF will not be employed.
Azilsartan and amlodipine besilate (hereinafter referred to as amlodipine) used before the start of treatment with Zacras	Antihypertensives other than Zacras that are terminated on the start day of treatment with Zacras or the previous day. Antihypertensives other than Zacras will be classified as described below based on the ingredients and their doses listed below. Fixed-dose combinations will also be classified based on individual ingredients and their doses. Azilsartan 20 mg, amlodipine 2.5 mg, amlodipine 5 mg, combined use of azilsartan 20 mg/amlodipine 2.5 mg, combined use of azilsartan 20 mg/amlodipine 5 mg, other
Switching to Zacras (by ingredient/dose)	Switching to Zacras will be classified as described below based on the combination of “azilsartan and amlodipine used before the start of treatment with Zacras” and “initial dose of Zacras.” Azilsartan 20 mg→Zacras LD, azilsartan 20 mg→Zacras HD, amlodipine 2.5 mg→Zacras LD, amlodipine 5 mg→Zacras HD, combined use of azilsartan 20 mg/amlodipine 2.5 mg→Zacras LD, combined use of azilsartan 20 mg/amlodipine 5 mg→Zacras HD, other
Switching to Zacras (by ingredient)	Switching to Zacras will be classified as described below based on “switching to Zacras (by ingredient/dose).” “Azilsartan→Zacras” for “azilsartan 20 mg→Zacras LD” or “azilsartan 20 mg→Zacras HD” “Amlodipine→Zacras” for “amlodipine 2.5 mg→Zacras LD” or “amlodipine 5 mg→Zacras HD” “Combined use of azilsartan/amlodipine→Zacras” for “combined use of azilsartan 20 mg/amlodipine 2.5 mg→Zacras LD” or “combined use of azilsartan 20 mg/amlodipine 5 mg→Zacras HD” “Other” for “other”
Patient who switches from combined use	Patient with “combined use of azilsartan/amlodipine→Zacras” for switching to Zacras (by ingredient)

Term	Definition
Duration of disease	(Start date of treatment with Zacras - time of diagnosis of hypertension + 1) $\div 365.25$. For time of diagnosis of hypertension, 1 will be used as the day, and January 1 will be used if the month is unknown. The duration of disease will be handled as missing if the year, month, and day are unknown.
ADR, etc.	Abbreviation of “adverse drug reaction/infection” AE other than those assessed by the investigator to be not related to Zacras In this document, “adverse drug reaction/infection” is used in titles, and “adverse drug reaction, etc.” is used in the text and tables.
SAE	Adverse event assessed by the investigator to be serious Events included in the MedDRA code list in Takeda Medically Significant AE List will be handled as serious even if assessed by the investigator to be non-serious.
Number of patients with an AE or an ADR, etc.	Number of patients who experienced an AE or an ADR, etc.
Number of AE or ADR, etc.	Number of reported AE or ADR, etc.
Time of onset	Time of onset will be calculated as date of onset of AE (or ADR, etc.) - start date of treatment + 1. If the month and day of AE (or ADR, etc.) are unknown, January 1 will be used for calculation. If an AE (or ADR, etc.) occurs in the same year as treatment is started, the month and day of starting treatment will be used for calculation. If the day of AE (or ADR, etc.) is unknown, 1 will be used for calculation. If an AE (or ADR, etc.) occurs in the same year and month as treatment is started, the start date of treatment will be used for calculation. If the year, month, and day of AE (or ADR, etc.) is unknown, the start date of treatment will be used for calculation.
Patient with concurrent diabetes	Patient with a check for diabetes in the column of concurrent illness in the CRF or concurrent illness corresponding to Standardised MedDRA query (hereinafter referred to as SMQ) code 20000041 (hyperglycaemia/new onset diabetes mellitus SMQ [scope: narrow]) described
Patient with concurrent dyslipidemia	Patient with a check for dyslipidemia in the column of concurrent illness in the CRF or concurrent illness corresponding to SMQ code 20000026 (dyslipidaemia SMQ [scope: narrow]) described
Patient with concurrent hyperuricemia	Patient with a check for hyperuricemia in the column of concurrent illness in the CRF or concurrent illness corresponding to MedDRA PT code 10020903 (hyperuricaemia) described

Term	Definition
Patient with concurrent cardiac failure	Patient with a check for cardiac failure in the column of concurrent illness in the CRF or concurrent illness corresponding to SMQ code 20000004 (cardiac failure SMQ [scope: narrow]) described in the column of other disease: name of disease
Patient with concurrent coronary artery disease	Patient with a check for myocardial infarction or angina in the column of concurrent illness in the CRF, concurrent illness corresponding to SMQ code 20000043 (ischaemic heart disease SMQ [scope: narrow]) described in the column of other disease: name of disease, or PT corresponding to SMQ code 20000047 (myocardial infarction SMQ [scope: narrow]) described in the column of medical history
Patient with concurrent myocardial infarction (including old myocardial infarction)	Patient with a check for myocardial infarction in the column of concurrent illness in the CRF or PT corresponding to SMQ code 20000047 (myocardial infarction SMQ [scope: narrow]) described in the column of other disease: name of disease or medical history
Patient with concurrent angina	Patient with a check for angina in the column of concurrent illness in the CRF or concurrent illness corresponding to MedDRA PT code 10002383 (angina pectoris), 10002388 (angina unstable), 10036759 (Prinzmetal angina), or 10058144 (postinfarction angina) described in the column of other disease: name of disease
Patient with concurrent coronary artery disease (other)	Patient with concurrent coronary artery disease who is not a patient with concurrent myocardial infarction (including old myocardial infarction) or angina
Patient with concurrent atrial fibrillation	Patient with a check for atrial fibrillation in the column of concurrent illness in the CRF or concurrent illness corresponding to MedDRA PT code 10003658 (atrial fibrillation) described in the column of other disease: name of disease
Patient with concurrent renal impairment	Patient with a check for chronic kidney disease (CKD), diabetic nephropathy, nephrosclerosis, or other in the column of concurrent illness in the CRF or concurrent illness corresponding to the following (1), (2), or (3) described in the column of other disease: name of disease: (1) SMQ code 20000213 (chronic kidney disease SMQ [scope: narrow]) (2) Takeda MedDRA query (hereinafter referred to as TMQ) (Renal Disease) (3) TMQ (Renal Impairment)
Patient with concurrent chronic kidney disease	Patient with a check for chronic kidney disease (CKD), diabetic nephropathy, nephrosclerosis, or other in the column of concurrent illness in the CRF or

Term	Definition
(CKD)	concurrent illness corresponding to SMQ code 20000213 (chronic kidney disease SMQ [scope: narrow]) described in the column of other disease: name of disease
Patient with concurrent diabetic nephropathy	Patient with a check for diabetic nephropathy in the column of concurrent illness in the CRF or concurrent illness corresponding to MedDRA PT code 10061835 (diabetic nephropathy) described in the column of other disease: name of disease
Patient with concurrent nephrosclerosis	Patient with a check for nephrosclerosis in the column of concurrent illness in the CRF or concurrent illness corresponding to MedDRA PT code 10029159 (nephrosclerosis) described in the column of other disease: name of disease
Patient with concurrent chronic kidney disease (CKD) (other)	Patient with concurrent chronic kidney disease (CKD) who is not a patient with concurrent diabetic nephropathy or nephrosclerosis
Patient with concurrent renal impairment (other)	Patient with concurrent renal impairment who is not a patient with concurrent chronic kidney disease (CKD), diabetic nephropathy, nephrosclerosis, or chronic kidney disease (CKD) (other)
Patient with concurrent hepatic impairment	Patient with a check for hepatic steatosis or alcoholic hepatopathy in the column of concurrent illness in the CRF or concurrent illness corresponding to the following (1), (2), or (3) described in the column of other disease: name of disease: (1) SMQ code 20000005 (hepatic disorders SMQ [scope: narrow]) (2) MedDRA PT code 10019708 (hepatic steatosis) MedDRA PT code 10001627 (alcoholic liver disease)
Patient with concurrent hepatic steatosis	Patient with a check for hepatic steatosis in the column of concurrent illness in the CRF or concurrent illness corresponding to MedDRA PT code 10019708 (hepatic steatosis) described in the column of other disease: name of disease
Patient with concurrent alcoholic hepatopathy	Patient with a check for alcoholic hepatopathy in the column of concurrent illness in the CRF or concurrent illness corresponding to MedDRA PT code 10001627 (alcoholic liver disease) described in the column of other disease: name of disease
Patient with concurrent hepatic impairment (other)	Patient with concurrent hepatic impairment who is not a patient with concurrent hepatic steatosis or alcoholic hepatopathy
Patient with concurrent cerebrovascular disorder	Patient with PT corresponding to SMQ code 20000060 (cerebrovascular disorders SMQ [scope: narrow]) described in the column of concurrent

Term	Definition
	illness: other disease: name of disease or medical history in the CRF
Age	If the month and day of starting treatment is smaller than the month and day of birth, age will be calculated as year of starting treatment - year of birth - 1. If the month and day of starting treatment is equal to or greater than the month and day of birth, age will be calculated as year of starting treatment - year of birth. If the month and day of birth is unknown, January 1 will be used for calculation. If the day of birth is unknown, 1 will be used for calculation.
Young, middle-aged, or young-old patient	Patient aged 15 years or older and 74 years or younger
Old-old patient	Patient aged 75 years or older
BMI	BMI will be calculated as body weight (kg) / [0.0001 × height (cm) × height (cm)]. BMI will be displayed to one decimal place by rounding.
Concomitant drug (at the start of treatment with Zacras)	Concomitant drug that is started before the start of treatment with Zacras and is not terminated on the day before the start of treatment with Zacras, or concomitant drug that is started on the start day of treatment with Zacras
Concomitant drug (during the survey period)	Concomitant drug used during a period from the start day of treatment with Zacras to the end day of treatment with Zacras
Concomitant drug (at the end of treatment with Zacras)	Concomitant drug used on the end day of treatment with Zacras
Antihypertensive used within 2 months before the start of treatment with Zacras	Drug described in the column for details on the use of other antihypertensive in the CRF that is started before the start day of treatment with Zacras and used within 2 months (60 days) before the start of treatment with Zacras (excluding drugs that are started on the start day of treatment with Zacras)
Antidiabetic	Drugs with a NHI drug code starting with 396, 2492, or 249941
Antidyslipidemic	Drugs with a NHI drug code starting with 218 or any of the following 7-digit numbers: 2190101, 2190102, 2190103, 2190104
Antihyperuricemic	Drugs with a NHI drug code starting with 394
Antihypertensive	ACE inhibitors, angiotensin receptor blockers (ARBs), diuretics (thiazide and thiazide analogue diuretics), calcium antagonists (hereinafter referred to as Ca antagonists), direct renin inhibitors, aldosterone antagonists/potassium-sparing diuretics, vasodilators, β -blockers, central sympathetic inhibitors, $\alpha\beta$ -blockers, α_1 -blockers, fixed-dose combination: ARB + diuretic, fixed-dose combination: ARB + Ca antagonist, fixed-dose

Term	Definition
	combination: Ca antagonist + statin, and fixed-dose combination: ARB + Ca antagonist + diuretic in a list of antihypertensives in the Guidelines for the Management of Hypertension 2014 (JSH2014)
ACE inhibitor	
Drugs described in the column for details on the use of other antihypertensive in the CRF that have a NHI drug code starting with the following 4-digit number:
 
2144
 
Generic name: captopril, enalapril maleate, perindopril erbumine, lisinopril hydrate, alacepril, delapril hydrochloride, benazepril hydrochloride, cilazapril hydrate, imidapril hydrochloride, temocapril hydrochloride, quinapril hydrochloride, trandolapril

ARB	
Drugs described in the column for details on the use of other antihypertensive in the CRF that have a NHI drug code starting with any of the following 7-digit numbers:
 
2149039, 2149040, 2149041, 2149042, 2149044, 2149046, 2149048, 2149110, 2149111, 2149112, 2149113, 2149119, 2149116, 2149114, 2149117, 2149118, 2149115, 2149120, 2149122
 
Generic name: losartan potassium, candesartan cilexetil, valsartan, telmisartan, olmesartan medoxomil, irbesartan, azilsartan, losartan potassium/hydrochlorothiazide, candesartan cilexetil/hydrochlorothiazide, valsartan/hydrochlorothiazide, telmisartan/hydrochlorothiazide, irbesartan/trichlormethiazide, candesartan cilexetil/amlodipine besilate, valsartan/amlodipine besilate, telmisartan/amlodipine besilate, irbesartan/amlodipine besilate, olmesartan medoxomil/azelnidipine, valsartan/cilnidipine, azilsartan/amlodipine besilate, telmisartan/amlodipine besilate/hydrochlorothiazide

Diuretic (thiazide and thiazide analogue diuretic)	
Drugs described in the column for details on the use of other antihypertensive in the CRF that have a NHI drug code starting with any of the following 7-digit numbers:
 
2132003, 2132004, 2132006, 2149103, 2149012, 2135001, 2149007, 2149003, 2149110, 2149111, 2149112, 2149113, 2149119, 2149122
 
Generic name: trichlormethiazide, hydrochlorothiazide, benzylhydrochlorothiazide, indapamide, mefruside, tripamide, meticrane, losartan potassium/hydrochlorothiazide, candesartan cilexetil/hydrochlorothiazide, telmisartan/hydrochlorothiazide, valsartan/hydrochlorothiazide, irbesartan/trichlormethiazide, telmisartan/amlodipine besilate/hydrochlorothiazide

Term	Definition
HCTZ	
Drugs described in the column for details on the use of other antihypertensive in the CRF that have a NHI drug code starting with any of the following 7-digit numbers:
 
2132004, 2149110, 2149111, 2149112, 2149113, 2149122
 
Generic name: hydrochlorothiazide, losartan potassium/hydrochlorothiazide, candesartan cilexetil/hydrochlorothiazide, valsartan/hydrochlorothiazide, telmisartan/hydrochlorothiazide, telmisartan/amlodipine besilate/hydrochlorothiazide

Dose of HCTZ	The dose of HCTZ is the maximum dose in patients receiving HCTZ.
Ca antagonist	
Drugs described in the column for details on the use of other antihypertensive in the CRF that have a NHI drug code starting with any of the following 7-digit numbers:
 
2171022, 2171014, 2171019, 2171020, 2149019, 2149022, 2149043, 2149027, 2149034, 2149037, 2149038, 2171021, 2149035, 2149030, 2171006, 2149116, 2149114, 2149117, 2149118, 2149115, 2190101, 2190102, 2190103, 2190104, 2149120, 2149122
 
Generic name: amlodipine besilate, nifedipine, nisoldipine, nitrendipine, nicardipine hydrochloride, nilvadipine, azelnidipine, manidipine hydrochloride, efonidipine hydrochloride ethanol, cilnidipine, aranidipine, benidipine hydrochloride, felodipine, barnidipine hydrochloride, diltiazem hydrochloride, candesartan cilexetil/amlodipine besilate, valsartan/amlodipine besilate, telmisartan/amlodipine besilate, irbesartan/amlodipine besilate, olmesartan medoxomil/azelnidipine, amlodipine besilate/atorvastatin calcium hydrate, valsartan/cilnidipine, telmisartan/amlodipine besilate/hydrochlorothiazide

